# **STUDY SUMMARY**

TITLE	A Randomised controlled trial of a sexual health promotion intervention for people with severe mental illness delivered in community mental health settings.
Acronym	moreRESPECT
Protocol Version	Version 1.5
Date	08/08/2024
ISRCTN	ISRCTN36391109
Study design	A two-arm, individually randomised controlled trial with internal pilot, embedded process evaluation and cost-effectiveness analysis
Study type and phase	Non-CTIMP. Phase III
Funder	National Institute for Health and Care Research Health Technology Assessment programme NIHR133865
Sponsor	Glasgow Caledonian University
Study Duration	49 months
Start date:	01/07/2023
Anticipated finish date:	30/06/2026
Study Centres	NHS community mental health services in England and Scotland
Objectives	To undertake a randomised controlled trial to determine whether a bespoke sexual health intervention is effective and cost-effective in reducing unprotected sexual acts, increasing knowledge about sexually transmitted diseases, motivation to engage in safer sex and condom use.
Study population	People with severe mental illness under the care of community mental health services
Target number of participants	400

Study groups	Control and intervention
	Control: Will continue to receive usual care for sexual health, a localised sexual health services leaflet and a sample pack of condoms.
	Intervention: Will continue to receive usual care for sexual health, a localised sexual health services leaflet, a sample pack of condoms and be offered 3x one-hour 1:1 manualized, theory driven sessions (either face to face or online via videoconferencing) with a health professional promoting sexual health.
Main Inclusion Criteria	People aged 16 or over currently in treatment with the community mental health services diagnosed with a severe mental illness. Willing and able to give informed consent (i.e., has capacity to consent).
	Exclusion: Lacking capacity to give informed consent; poses a risk to others (including risk of sexual/physical violence); a co-existing learning disability of other significant cognitive impairment; those on sex offenders register
Primary outcome measure(s)	Number of unprotected sex acts (anal, vaginal, oral) recorded every three months (at 3, 6, 9 and 12 months) over the 12-month follow-up using the Sexual Risk Behaviour Assessment Schedule (SERBAS).
Secondary outcome measure(s)	Knowledge about human immunodeficiency virus (HIV) and sexually transmitted infections using the HIV Knowledge Questionnaire (HIV-KQ), Motivation to Engage in Safer Sex, Condom use Self-Efficacy Scale, Behavioural Intentions for Safer Sex, Quality of life (QoI) using the EQ-5D-5L and Recovery QoL (ReQoI) measures, General questions about sexual health (items adapted from the National Surveys of Sexual Attitudes and Lifestyles (NATSAL), and health care resource use
Other outcome measure(s)	A process evaluation will be conducted with a small group of participants to find out how they found the support package and whether it worked better for some than others and in what circumstances.
	An economic evaluation will be undertaken from the perspective of the NHS and personal social services.

#### **PLAIN ENGLISH SUMMARY**

People with severe mental illness (SMI) have significant needs in terms of physical health compared to the general population. Initiatives have commenced to address this; however, sexual health has been missed off the agenda. Like everyone else, positive sexual relationships are important for people with SMI, but this is rarely discussed in routine mental health care. Therefore, they can be unaware of important information such as where to get sexual health advice, how to reduce risk of sexually transmitted infections, contraceptive choices and finding relationships that are mutually respectful, not violent or abusive.

In a National Institute for Health and Care Research (NIHR)-funded feasibility study, this research team developed a 3-session support package that helped people with SMI to think about their own sexual health and provided useful information about how to improve their sexual health. Following the success of the feasibility study, this full trial will examine the effectiveness and cost-effectiveness of the intervention by recruiting 400 people with SMI from National Health Service (NHS) community mental health teams across England and Scotland.

People who agree to take part will be randomly allocated to either usual care (control arm) or usual care plus the moreRESPECT intervention (intervention arm). Data will be collected at baseline and then at 3-, 6-, 9- and 12 months post-randomisation. As part of a nested process evaluation, interviews with a small group of participants will also be conducted at 6 months post randomisation to find out how they found the support package and whether it worked better for some than others and in what circumstances.

# PROTOCOL AMENDMENT HISTORY

Protocol version and date	Amendment number and ethics approval date	Details of changes made
1.1 16/06/2023	N/A – Amendments made in response to REC / HRA and other minor updates after initial IRAS submission Approved by REC / HRA on 05/07/2023	
 
Combined participant identification routes '3) Direct route to moreRESPECT study team' and '4) Direct approach in clinics' since they use the same principles of study promotion. It is now referred to as '3) Study promotion and self-referral to moreRESPECT study team (pg 19-20). It has also been made clear that the MR researcher or members of the NHS sites R&D research team will only only directly approach if the potential participant has given verbal consent for a researcher to talk to them about the study (pg 20).
 
Updated the wording of the responsibilities of the MR researcher and R&D staff based on the above update (pg 12).
 
Added that audio files will be deleted after transcription has been checked for accuracy and any typos corrected (pg 33).
 
The organisation of co-applicant [name] was corrected from 'Kings College Hospital NHS Foundation Trust' to 'Guy's and St Thomas NHS Foundation Trust (pg 11).
 

1.2 21/09/2023	Non-Substantial Amendment 4 - Updates to trial documents: Approved by HRA on 03/10/2023  Substantial Amendment 1 - Change in Sponsor name: Approved by REC / HRA on 13/10/2023	Change of Sponsor and CI/Intervention Lead place of work: Replaced Edinburgh Napier University logo/details with Glasgow Caledonian University logo/details.
1.3 06/06/2024	Non-Substantial Amendment 8  Approved by HRA on 20/06/2024	
 
Timing of intervention delivery added to be delivered before the 3 month follow up.
 
The inclusion criteria has been revised to allow the recruitment of participants from inpatient units if they are due for discharge but remain in inpatient care due to the unavailability of suitable community placements.
 
Added clarification to confirm that the inclusion criteria 'Willing and able to give informed consent to participate' is about capacity, not consent.
 
Added clarification on what will be accepted as a valid consent form.
 

1.4 10/07/2024	Non-Substantial Amendment 9 Approved by HRA on 18/07/2024	
 
To support remote data collection the interview version of the EQ-5D-5L has been added to the researcher CRF at baseline and all follow ups. The self-complete version of the EQ-5D has been removed from the participant completed baseline CRF and all follow ups.
 
The protocol has been updated to reflect this.
 

1.5 08/08/2024	Non-Substantial Amendment 11	Added clarification of how consent, baseline data collection and follow-up data collection can be conducted, which includes face to face or remote (online videoconferencing/telephone) methods.

# **LIST OF COMMON ABBREVIATIONS**

AE	Adverse event
AUC	Area under the curve
CEACs	Cost effectiveness acceptability curves
Cl	Chief Investigator
CRF	Case report form
CRN	Clinical Research Network
DMC	Data Monitoring Committee
GCP	Good Clinical Practice
HEAP	Health economics analysis plan
HIV	Human Immunodeficiency Virus
HIV-KQ	Human Immunodeficiency Virus Knowledge Questionnaire
HPV	Human Papilloma Virus
HRA	Health Research Authority
LEAG	Lived Experience Advisory Group
LGBTQ	Lesbian, Gay, Bisexual, Transgender, Queer
MRC	Medical Research Council
NATSAL	National Surveys of Sexual Attitudes and Lifestyles
NHS	National Health Service
NIHR	National Institute for Health and Care Research
PIS	Participant information sheet
PPI	Patient and public involvement
PSSRU	Personal Social Services Research Unit

People with lived experience
Quality adjusted life years
Quick response
Randomised controlled trial
Research Ethics Committee
Recovering Quality of Life
Research and Development
Serious Adverse Event
Sexual Risk Behaviour Assessment Schedule
Severe mental illness
Standard operating procedure
Thematic Analysis
Trial Management Group
Trial Steering Committee
York Trials Unit

 $more RESPECT\_Protocol$ 

# 1.3 Researcher titles, roles and responsibilities

Researcher title:	Based at:	Responsibility:	Access to data:	Blinded to participant
				allocation:
moreRESPECT researcher	Site or University employed	
 
Promote study in public areas of NHS sites such as waiting rooms, communal areas, with prior permission of clinical team
 
Speak to potential participants patients who have given consent to be contacted,
 
Obtain informed consent
 
Conduct baseline and follow-up assessments
 
Complete the MR Researcher interview CRF including the SERBAS questionnaire
 
(if in clinic) confirm completion of the Participant self-completed CRF
 
Post completed CRFs to YTU
 
Conduct reminder telephone calls with participants who have not completed their CRF
 
Complete change of status and AE forms and notify YTU
 
	- Consent form and consent to contact forms - Participant CRFs - Patient identifiable data	Yes
R&D staff	Site	
 
Promote study in public areas of NHS sites such as waiting rooms, communal areas, with prior permission of clinical team Maintain and update a record sheet of patients enrolled at site
 
Post completed CRFs to YTU
 
Maintain a file of essential trial documentation
 
	
 
Participant allocation
 
Consent form and consent to contact forms
 
Participant CRFs
 
Patient identifiable data
 
	No
YTU staff  moreRESPECT Pro	YTU	
 
Conduct randomisations
 
Inform participant, sites, MR researcher, lead interventionist (if applicable), participants GP and participants NHS care provider of participant randomisation
 
Support day to day trial management and monitoring activities
 
Conduct site set-up
 
 RAS ID: 309345 REC Reference: 23/NW/02	- Participant allocation - Consent form and consent to contact forms - Participant CRFs - Patient identifiable data	No

moreRESPECT\_Protocol

IRAS ID: 309345

REC Reference: 23/NW/0157

		Provide trial Standard Operating     Procedures     File, process and analyse patient and researcher data		
Intervention lead	Glasgow Caledonian University	
 
Work with sites to provide training and supervision for interventionists
 
Coordinate the allocation of an interventionist to a participant - Confirm interventionist and participant pairings to YTU
 
Deliver monthly supervision groups online with interventionists
 
	

Participant allocation

Patient identifiable data

	No
Interventionist	Site	
 
Complete intervention training
 
Conduct intervention
 
Send reminders.to participants regarding future sessions
 
Attend monthly supervision with intervention lead
 
	

Participant allocation

Patient identifiable data

	No

REC Reference: 23/NW/0157

[figure not shown]

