# 8. Recruitment

#### 8.1 Source

From the work conducted in the feasibility study, it was found that having multiple routes into the study is important. Potential participants will be identified via three main routes.

1) Caseload screening and promotion within the community mental health teams:

People will be identified via screening of caseload records by a person designated to this task within the NHS organisation. They will work with the clinically facing NHS staff in community teams to promote the study and undertake caseload screening for potentially eligible participants using the eligibility criteria outlined above. Once someone has been

identified as potentially eligible, clinically facing NHS staff will be asked to distribute information to them. This initial information will consist of an emailed PDF or printed version of the study leaflet which will include the study teams contact details and a quick response (QR) code for linking to the study website. The website has been designed to provide detailed information about the study for both staff and potential participants, as well as other interested parties. The website will contain information in a user-friendly format and this will have an in-built translation software tool so that all the information about the study including a web-based PIS and Consent Form can be translated into any language. A potential participant can directly contact the study team via email by completing a form on the website. If the patient expresses an interest in finding out more about the study, they will be provided with an information pack (invitation letter, patient information sheet (PIS) and consent to contact form). This pack can be either accessed directly from the study website, face to face by their NHS care provider, the sites NHS R&D staff or the moreRESPECT researcher (MR researcher), or posted to their home address from their NHS care provider. If after reading the materials they are interested in hearing more, they will be asked to give consent to be contacted for a further discussion. This consent to contact can be done via the study website "contact us" section; returning a completed form (by post or email) or verbally (and documented by site NHS staff). The MR researcher then will make contact with the potential participant to discuss the study and obtain informed consent.

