## 3) Study promotion and self-referral to moreRESPECT study team:

Self-referral will be possible via the study website, which will be promoted online via social media and also in areas where potential participants congregate at NHS services, such as communal areas, waiting rooms, local service user groups, clozapine clinics or local voluntary sector organisations through posters and leaflets. Prior permission will be obtained from the clinical team in clinics/wards for the MR researcher or members of the

NHS sites R&D research team to display study posters and offer the study leaflet in person. If a patient who is attending a clinic wishes to ask any questions, then they will be able to discuss the study informally face to face with the MR Researcher or R&D research team member who is present. They will only directly approach a potential participant if they have given verbal consent for a researcher to talk to them about the study. Potential participants will not be under any obligation to decide to participate at this time. This approach was used for recruitment in the RESPECT Feasibility study and was effective as well as being acceptable to potential participants. Our Lived Experience Group also advocated for this approach as an acceptable way of promoting the study.

The study poster and leaflet will contain details of how to get in touch with the study team as well as a link (QR code) to the website which has more information about the study including the PIS. A potential participant can directly contact the study team via email by completing a form on the website. All self-referrals will be informed that the MR researcher will pass on their name to their NHS care provider to complete an eligibility check and once this is confirmed, the MR researcher will make contact with the potential participant to discuss the study and obtain informed consent. The MR researcher will be responsible for ensuring that the potential participant has accessed the digital versions of the PIS online, and if not, will be able to email this document. Self-referring participants will be unable to participate in the study without an eligibility check that has been completed by their NHS care provider.

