#### 8.4 Randomisation and blinding

Randomisation will be undertaken by a MR researcher (who will be blinded to allocation) or member of staff at YTU working on the study via a trial management system built by YTU. The allocation sequence will be generated by an independent statistician at YTU who is not involved in the recruitment of participants. Participants will be randomised on a 1:1 basis to either usual care or intervention plus usual care. Stratified block randomisation will be used, with the NHS site as the stratifying variable, and randomly varying block sizes, to ensure even allocation to intervention across sites.

The following information will be collected for each participant at baseline, prior to randomisation:

- Site the participant belongs to;
- NHS community mental health service that provides the participants care;
- Participants details including full name, date of birth, full postal address, contact telephone number(s) and email address;
- Participants GP details including practice name, postal address and where possible contact telephone number(s) and email address
- Participants NHS Care provider details including full name, postal address and where possible contact telephone number(s) and email address
- Both the MR researcher interview and participant self-completed baseline CRFs completed and returned to YTU (see section 10.4 Data collection schedule)
- · Confirmation that patient meets all the eligibility criteria
- Confirmation that informed consent has been obtained
- Confirmation if they can be contacted for qualitative interviews
- Confirmation if they would like to be sent a plain English summary of results
- Confirmation if they can be contacted for future studies.

To keep the MR researcher blinded to the allocation, the YTU will inform the participant of their allocation, and arrangements for the intervention delivery if allocated to this, via letter generated from the trial management system. YTU will alert the intervention coordinator/lead that there is a new participant and securely pass on the name and contact details either via moreRESPECT Protocol IRAS ID: 309345 REC Reference: 23/NW/0157 Version 1.5 08/08/2024

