#### 15. Data handling, management and storage

Information with regards to the study participants will be kept confidential and managed in accordance with the Data Protection Act, NHS Caldicott Guardian, UK Policy Framework for Health and Social Care Research and the Health Research Authority.

Data management will ensure that each site and study participant is assigned a unique trial identification number at the start of data collection; all data (paper and electronic) will use this unique trial identification number. A record sheet linking patient identity, contact details and trial identification number for all participants will be kept at each site. This will be placed securely in a locked filling cabinet, separate from datasheets.

moreRESPECT\_Protocol

IRAS ID: 309345

REC Reference: 23/NW/0157

Identifiable data of consenting participants will be stored on paper and on a secure password protected electronic server at the University of York, for the purposes of assisting in follow-ups during the study. Personal data will be stored separately to the trial data. Study data will be collected using anonymous paper CRFs, which will be completed by both the MR researcher and the participant and returned to YTU via post. Paper CRFs collected from participants will be kept in a safe, secure environment (locked drawer in a locked office) by the MR researchers and posted as soon as possible to the YTU. Analytical datasets will not contain any identifiable information. The data management system, CRFs, identifiable data and non-identifiable data will be stored securely for up to 10 years after the end of the trial and then destroyed securely in accordance with the current YTU Standard Operating Procedures. Consent forms will be stored up to 6 years after the end of the trial and then destroyed, as allowed by the Prescriptions and Limitations Act.

All data will be kept secure at all times, maintained in accordance with the requirements of GDPR and archived according to Good Clinical Practice (GCP) regulations. Paper data collection forms transferred to or from the YTU will be coded with a participant ID. Data will be held securely on paper and electronically at YTU and appropriate processes put in place for the transfer, storage, restricted access, and disposal of personal information. Relevant Standard Operating Procedures (SOPs), guidelines, and work instructions in relation to data management, processing, and analysis of data will be followed.

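### Site R&D staff who help recruit also have access to allocations, so with blocks stratified by site the next allocation becomes partly predictable when patients are approached

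*Protocol*

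**What the plan says.** **Access.** In the role table of protocol section 1.3, the row for R&D staff (based at the site) lists "participant allocation" under access to data and gives No in the blinding column.

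**Duties.** The same row has these staff promote the study, "with prior permission of clinical team Maintain and update a record sheet of patients enrolled at site", where two bullets have merged in the text. They also post completed CRFs to YTU and maintain the trial file.

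**Contact with potential participants.** Under route 1 of section 8.1, those who may hand over the information pack face to face include "the sites NHS R&D staff or the moreRESPECT researcher". Under route 3, if patients attending a clinic have questions, "they will be able to discuss the study informally face to face with the MR Researcher or R&D research team member who is present".

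**Randomisation.** Section 8.4 states: "Stratified block randomisation will be used, with the NHS site as the stratifying variable, and randomly varying block sizes". Allocation is 1:1. An independent YTU statistician generates the sequence, and a blinded moreRESPECT (MR) researcher or YTU staff randomise through YTU's system. Confirmed eligibility, confirmed consent and both baseline CRFs are required first.

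**Who else is told.** Under section 8.4, YTU informs the participant and the intervention lead, and the lead assigns the interventionist. GPs and care providers are not told the allocation, and interventionists may not pass it to MR researchers. The section does not mention what R&D staff know.

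**The concern.** Blocks balance the arms at short intervals within each site, so past allocations carry information about the next one. Randomly varying block sizes reduce that information but do not remove it. The protection depends on people with influence over recruitment not seeing the running list at their site. The protocol blinds the MR researcher who takes consent, yet it gives access to allocations to a staff group that may speak to patients before they reach that researcher.

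If someone used that knowledge, even informally, to choose whom to encourage or when, the arms could differ at baseline in sexual activity or willingness to engage. Covariate adjustment may not fully repair such a difference. The protocol gives no sign that staff would do this. The point is that the route is open, has no stated purpose and is cheap to close.

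**Working it through.** **1. Do the listed duties need the allocation?** Taking the R&D duties in section 1.3 in turn:
- Promotion: no.
- Record of enrolled patients: no. Section 15 describes the sheet thus: "A record sheet linking patient identity, contact details and trial identification number for all participants will be kept at each site". Allocation is not among its contents.
- Posting CRFs: no.
- Trial file: no use of individual allocations is stated.

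Section 8.4 gives R&D staff no step in telling participants or in pairing them with interventionists.

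**2. How predictable is the next allocation?** The protocol gives no figure for this and no block sizes, so there is nothing to reproduce and the sizes must be assumed.

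Inputs: target 400 (section 9); 12 localities recruiting at a time, a site being defined as a locality (section 6.2); 1:1 ratio and varying blocks (section 8.4). Average per site: 400/12 = 33.3, taken as 33.

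Model: each block size is drawn with equal probability from the assumed set and each block is shuffled. The observer sees every past allocation at the site and knows the set of sizes, but not the size drawn. For each possible state of the current block, with l0 control and l1 intervention places left and posterior weight w,

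P(next is intervention) = sum of w × l1/(l0 + l1).

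The observer guesses the more likely arm (a coin toss if equal) and updates w after each allocation. Results over 2,000 simulated sites of 33:

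| Block sizes (assumed) | Guessed correctly | Known with certainty |
|---|---|---|
| 2, 4 | 71.7% | 10.7% |
| 2, 4, 6 | 69.8% | 3.6% |
| 4, 6 | 68.4% | 5.6% |
| 4, 6, 8 | 67.3% | 2.4% |
| 6, 8, 10 | 65.5% | 1.6% |
| fixed 4 (comparison) | 70.1% | 32.4% |
| allocations withheld | 50% | 0% |

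A cruder rule, always guessing the arm with fewer allocations so far, gives almost the same rates over 4,000 sites: 71.5% (2, 4), 69.5% (2, 4, 6), 68.5% (4, 6) and 67.3% (4, 6, 8). No sophistication is needed.

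**3. Hand check on the fixed block of 4.** The four positions are guessed correctly with probability 1/2, 2/3, then 1/3 × 1 + 2/3 × 1/2 = 2/3, then 1. The sum is 17/6. Thirty-three participants make eight full blocks plus one, so (8 × 17/6 + 1/2)/33 = 70.2%, against 70.1% simulated. Certain positions per block: 1/3 + 1 = 4/3, so (8 × 4/3)/33 = 32.3%, against 32.4%.

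**4. In participants per site.** Chance gives 16.5 of 33. The excess is (0.66 - 0.50) × 33 = 5.3 to (0.72 - 0.50) × 33 = 7.3 correct guesses. Certainty covers 0.02 × 33 = 0.7 to 0.11 × 33 = 3.6 participants.

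**The case against.** A reader might infer that allocation concealment can be broken. The protocol does not support that. The sequence is generated by a statistician with no part in recruitment, randomisation runs through YTU, and R&D staff neither take consent nor randomise. Varying the block sizes cuts certainty from about 32% (fixed block of 4) to about 2-11%.

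A guess is also hard to use. Eligibility, consent and return of the baseline CRFs, which travel by post, all come between approach and randomisation, and others at the site may be randomised meanwhile. R&D staff are one channel among several: a designated person screens caseloads, clinical staff give out the first information, and R&D staff approach a patient directly only after verbal agreement.

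A reader might also infer that these staff see every allocation at their site. The table names a type of data for a role. It does not say how much of it, how promptly, or whether the person who sees it is the person in the clinic. Nor does the record sheet reveal allocation, on the description in section 15.

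Finally, a site may have a legitimate need. Section 1.3 has YTU inform sites of randomisation, and section 11.1 requires protected time for interventionists.

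All of this stands, and it limits the size of the problem. It does not explain why staff with recruitment contact need the access, and nothing in the protocol separates the two roles.

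**Conclusion.** The point holds as an avoidable weakness at the approach stage. Section 1.3 allows unblinded site staff with access to allocations to take part in recruitment within the stratum in which the blocks run.

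The guess rates of about 66-72% are a ceiling on usable foreknowledge, not an estimate of bias. They assume block sizes that the protocol does not state, about 33 participants per site, one observer who follows every allocation in order, and each guess applied to the very next person randomised. Strata may be smaller than 33, since section 6.2 allows further organisations to join. No baseline imbalance or distortion of the incidence rate ratio can be derived from the document. Not stating block sizes in a protocol is no fault. The change is worth making because it is cheap, not because the trial's concealment has failed.

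**What to change.** In the section 1.3 table, and in the permissions of the trial management system, remove access to allocation from R&D staff who promote the study, give out packs or discuss it with patients, and show them as blinded. Where a site must hold allocations, for example to arrange interventionists' protected time, limit this to an existing staff member with no recruitment contact, and say so in section 8.4. The site record sheet needs no change.

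The cost is a wording change to the role table and a permissions change. Some site queries about allocation will then have to go through YTU.
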